
15. HIPAA

HIPAA authorization is required given the PHI that is acquired during the study procedures. The HIPAA form will be discussed verbally after it is determined the participant is eligible from the phone screen inclusion and exclusion criteria. The HIPAA form will be electronically signed via DocuSign at this time.

16. Data Analysis Plan

Our enrollment goal is 36 patient-caregiver dyads over a 9-month enrollment period. We expect attrition will occur over the 12-week intervention period. Given a sample size of 15 patient-caregiver dyads, our aim to detect a statistically significant change in physical activity from baseline to POST will be adequately powered ($\alpha = .05$, $1-\beta = .8$) to detect an effect size of approximately $d = 1.06$. Assuming a SD of approximately 36% and stable control group activity, this would reflect an approximate 35% increase in steps from baseline to post-intervention. Daily step changes between groups will be compared using a 2 x 2 repeated measures ANOVA, testing for main effects of group and time, and the interaction effect between groups across time. This analysis assumes no missing data for the 15 patient-caregiver dyads – in the event of greater than expected attrition occurs, we will use a mixed model to estimate from all available data on an ‘intent to treat’ basis. Similar analyses will be performed for all other quantitative outcomes described in the Participant Duration section.

Directed content analysis⁵⁵ will be used to assess the qualitative data gathered from semi-structured interviews. Savin-Baden⁵⁶ outlined three steps to qualitative research: (1) visually familiarize yourself with the data by reading the transcripts, then identify primary categories, (2) generate conclusions, and (3) check the results. will be analyzed by determining common themes across. The 14 domains of the Theoretical Domains Framework (TDF) will be used as a priori codes to classify the barriers and facilitators discussed by participants. The 14 domains in the TDF are: knowledge; skills; social/professional role and identity; beliefs about capabilities; optimism; beliefs about consequences; reinforcement; intentions; goals; memory, attention, and decisions processes; environmental context and resources; social influences; emotion; and behavioral regulation.⁵⁷ The TDF domains will be used as the “primary categories” (i.e. a priori codes) to capture participants’ responses to the feasibility of the intervention to achieve improvement in daily stepping (step 1). The researcher will then read through the coded data as well as the data that was not coded to generate conclusions and construct themes related to the feasibility of the intervention to achieve improvement in daily stepping (step 2). Finally, the themes and raw data supporting each theme will be reviewed by the researcher with attention to an accurate representation of participants’ perceptions of intervention feasibility (step 3). To enhance rigor, we will consider procedures to promote credibility, consistency, and transferability.⁵⁸ First, to ensure credibility we will triangulate between data sources (interviewers notes, transcripts, and interdisciplinary discussion). Secondly, to enhance consistency, the researcher who is coding will keep an audit trail of all decisions related to coding, interpretation, and constructed themes.

REFERENCES

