4. Study Population:

Thirty-six individuals with probable amnesic MCI between the ages of 50-85 years old and informal caregivers (19+ years of age) from the Omaha metro and surrounding areas will be recruited to participate in this study. The spectrum of amnesic MCI allows individuals that may or may not be able to give consent and is needed for this study to best reflect individuals with amnesic MCI. If the patient is unable to give consent per research team assessment, a legally authorized representative will be present and sign the consent form and the patient will verbally assent. Additionally, patients will be monitored and withdrawn if they appear to be unduly distressed from participating in the study. Due to anticipated attrition, we plan on recruiting 36 patient-caregiver dyads (18 dyads per group) to meet the necessary 15 dyads per group for statistical purposes. A sample size of 15 patient-caregiver dyads per group will meet our aim to determine a statistically significant change in activity from baseline to post-intervention (13 weeks) with adequate power ($\alpha = .05$, $1-\beta = .8$) ability to detect an effect size of approximately $d = 1.06$.

5. Inclusion/Exclusion Criteria

Inclusion criteria for participants with probable amnesic MCI are: 1) 50-85 years old, 2) memory impairment as demonstrated with deficits in the memory domain scores on the Montreal Cognitive Assessment (MoCA), 3) a score of 18-24 on the MoCA indicating possible MCI,²⁹ 5) not currently categorized as “Active” on the Rapid Assessment of Physical Activity,³⁰ 6) have a primary caregiver willing to participate in physical activity and assist the patient with participation in the study. Inclusion criteria for both the patient and caregiver include: 1) self-reported household ambulator, 2) on stable doses of medication at least for the previous 30 days at baseline, 3) have a computer/wireless device with Internet access, 4) English-speaking. Caregiver must additionally score 24 or higher on the Mini-Mental Status Exam (MMSE) indicating no impairment to be included in the study³¹ and be 19+ years of age. If the caregiver does not meet this requirement the patient will be asked if there is another caregiver willing to participate in the study.

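### Section 16 converts d = 1.06 at a 36% SD into a 35% step gain, but the product is about 38%, and the plan does not say which SD the 36% is

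*Combined protocol and SAP*

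**What the plan says.** Section 4 (Study Population) plans 36 dyads, 18 per group, so that 15 per group remain after attrition. It states: "A sample size of 15 patient-caregiver dyads per group will meet our aim to determine a statistically significant change in activity". It attaches alpha .05, 80% power and d of about 1.06 to that number.

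Section 16 (Data Analysis Plan) repeats the claim without the words per group: "Given a sample size of 15 patient-caregiver dyads, our aim to detect a statistically significant change in physical activity from baseline to POST". It gives the same alpha, power and d, and then translates the effect size into steps: "Assuming a SD of approximately 36% and stable control group activity, this would reflect an approximate 35% increase in steps from baseline to post-intervention".

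The analysis named in Section 16 is a 2 x 2 repeated measures ANOVA of daily steps with a group-by-time interaction. The hypothesis in Section 11 is a gain in the intervention group relative to control. Neither section says whether the 36% is the SD of change or of step level, and neither gives a baseline-post correlation.

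**The concern.** The Section 16 sentence takes three linked quantities, an effect size, an SD and a percentage gain, and any two of them fix the third. The three printed values do not fit together on the plain reading.

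The 35% is the only place where the plan states its detectable effect in steps, the unit of Aim 2. Section 8 says the study can provide data for a larger efficacy study. A planner would take from Section 16 that a 35% gain had an 80% chance of being detected here. On the plain reading the chance is about 73%, so the risk of missing such a gain is about 27% rather than 20%.

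**Working it through.** **Inputs.** Alpha .05, power .80, d = 1.06 and 15 dyads per group (Sections 4 and 16, with per group only in Section 4); SD 36%, control change 0% and gain 35% (Section 16). Sidedness is not stated.

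**1. Reproduce the plan's d.** In a 2 x 2 design the group-by-time test is equivalent to a two-sample t test on change scores. With n per group, df = 2n - 2 = 28 and the noncentrality is d x sqrt(n/2). At n = 15 and d = 1.06 this is 1.06 x sqrt(7.5) = 2.90. Two-sided power from the noncentral t is 80.0%, and the d that gives exactly 80% is 1.060. The stated figure reproduces.

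Other calculations do not give 1.06:

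| Calculation | Detectable d at 80% power |
|---|---|
| Two-sample t, two-sided, 15 per group | 1.06 |
| Normal approximation, two-sided, 15 per group | 1.02 |
| Two-sample t, one-sided, 15 per group | 0.93 |
| Paired t within one group, n = 15 | 0.78 |
| Two-sample t, 15 dyads in total (7 and 8) | 1.57 |

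So d = 1.06 is a between-group effect, two-sided, with 15 in each group.

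**2. Convert to steps.** With no change in controls, gain = d x SD = 1.06 x 36% = 38.2%.

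**3. Test whether rounding explains 35%.** The smallest inputs that round to the printed values are 1.055 and 35.5%, and 1.055 x 35.5% = 37.5%. To reach 35% at d = 1.06 the SD would have to be 35/1.06 = 33.0%.

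**4. Power for 35% if 36% is the SD that standardises d.** d = 35/36 = 0.972, and the noncentrality is 0.972 x sqrt(7.5) = 2.66. Power at 15 per group is 72.9%. Letting the gain run from 34.5% to 35.4% and the SD from 35.5% to 36.5%, power runs from about 70.5% to 75.1%.

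**5. If 36% is the SD of step level (assumption).** With equal SDs at both times, the SD of change = 36% x sqrt(2(1 - r)), where r is the baseline-post correlation.

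| r (assumed) | SD of change | Detectable gain (1.06 x SD) | Power for 35% |
|---|---|---|---|
| 0.3 | 42.6% | 45% | 58% |
| 0.5 | 36.0% | 38% | 73% |
| 0.7 | 27.9% | 30% | 91% |

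The 35% is recovered when the SD of change is 33.0%, that is at r = 1 - (33.0/36)^2 / 2 = 0.58.

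**The case against.** The strongest defence is that the plan's power claim is attached to d = 1.06, and that claim is correct. The 35% is an illustration that follows it. Nothing in the document derives the sample size from 35% or names it as the target. This stands: the error lies in the conversion, and 73% is the answer only to the question of what power a 35% gain would have.

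A second defence is that 36% may be the between-person SD of steps, in which case a correlation of about 0.58 makes the sentence exact. This also stands as a possibility, so 38% and 73% cannot be stated without a condition. It does not rescue the text, because no correlation is given and the result moves from 45% to 30% over r = 0.3 to 0.7.

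Third, Aim 2 concerns preliminary effects, all three figures are marked as approximate, and a null result would be interpreted from its confidence interval rather than from a planning sentence. That lowers the severity, but the discrepancy exceeds rounding.

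Fourth, per group is explicit in Section 4, and the between-group intent is clear from the hypothesis in Section 11 and from the phrase "stable control group activity". The wording faults in Section 16 are therefore matters of clarity and do not show that a different analysis is planned.

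A reader might also infer that the 35% was worked out for all 18 enrolled dyads per group, since 18 per group detects d = 0.961, and 0.961 x 36% = 34.6%. The document does not support this. It shows no power calculation at 18, which appears only as the recruitment number that allows for attrition. An SD of 33% or a correlation of 0.58 fits equally well.

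**Conclusion.** The conversion in Section 16 does not follow from its own inputs. The stated d and SD give 38.2%, at least 37.5% after rounding, against a printed 35%. If 36% is the SD that standardises d, which is the plain sense of the sentence, a 35% gain has about 73% power at 15 per group, a shortfall of about 7 percentage points. This rests on a two-sided two-sample t test, the only variant checked that reproduces d = 1.06, and on no change in controls.

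A reader might go further and conclude that the trial is underpowered against its own target, or that its sample size is wrong. The document does not support that: 80% power for d = 1.06 is correct, and 35% is not set as a design target. Nor does it establish that 36% is the SD of change. What holds is that the SD is undefined and that d, SD and gain do not agree as written. Severity is moderate to minor.

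**What to change.** In Section 16:

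- Write 15 dyads per group.
- Describe d = 1.06 as the between-group difference in change from baseline, two-sided.
- State whether 36% is the SD of change or of step level. If it is the SD of step level, give the assumed baseline-post correlation and its basis.
- Restate the detectable gain to match. If 36% is the SD of change, suitable text is: *With 15 dyads per group (two-sided alpha .05, 80% power), the detectable between-group difference in change is d = 1.06, about 38% of baseline steps if the SD of change is 36% and control activity is stable; power for a 35% difference is about 73%.* If 36% is the SD of step level, give the gain as 1.06 x 36% x sqrt(2(1 - r)) at the stated r.

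Use the same between-group wording in Section 4.

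The sponsor has to supply the definition of the SD, since the document does not allow a reviewer to choose it. The cost is a few sentences and, if 36% is the SD of change, a slightly less favourable stated figure. The sample size, test and feasibility criteria do not change, and no extra patients are needed.

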undergraduate students assisting with the research witness events, they deem reportable, they will discuss with the PI ([name]) to determine what agency should receive the report, if necessary. The testing procedures are detailed below and will take approximately 2 hours to complete at each testing time point (baseline and post-intervention). The TPAB intervention will involve weekly 30-minute sessions with [name] for 12 weeks. The details of information covered during the TPAB intervention sessions are outlined in the Intervention Checklist attachment. For the TPAB intervention group, all participants (patients and caregivers) will be provided a Fitbit. Directions on how to interact with the Fitbit app will be discussed during the first intervention session and are detailed in the Patient-Workbook attachment. It is expected that participants will return the provided Fitbit at the end of their study participation. Due to the 7-day activity monitor data collection prior to and following the 12-week TPAB intervention, participants will be enrolled in the study for approximately 14 weeks.

To assess Aim 1, we will measure retention, attendance, acceptability, safety, and qualitative feasibility perspectives. Based upon previous research, we expect to retain at least 85%³³ and attendance of at least 80%³⁴ to deem the study a success. The TPAB intervention will be regarded as acceptable with a mean of >5.0 (null value)³⁵ on the Intrinsic Motivation Inventory – Interest / Enjoyment Subscale.²⁸ The number of adverse events in the TPAB intervention group will be similar to that of the control group and will not exceed five adverse events related to the TPAB intervention. Finally, qualitative feasibility data will be gathered via audio recorded semi-structured interviews.

To assess Aim 2, we will measure daily steps at baseline and post-intervention. Daily steps will be measured across seven days at each time point (from the activPAL). Refer to ActivPAL instructions attachment for more details about activity monitor placement. Previous work has shown individuals with MCI can reliably and feasibly wear activity monitors.^{7, 36, 37} We hypothesize that the TPAB intervention group will make significant gains in daily steps from baseline to post-intervention compared to the control group.

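### The Aim 2 test of daily steps compares change scores and does not adjust for baseline steps; a baseline-adjusted group contrast is a nearly free gain in precision, of a size that depends on an unstated correlation.

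*Combined protocol and SAP*

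**What the plan says.** Section 3 (Aim 2) asks about the preliminary effect of TPAB on daily steps in MCI participants relative to control. Section 11 gives the hypothesis: "We hypothesize that the TPAB intervention group will make significant gains in daily steps from baseline to post-intervention compared to the control group". Daily steps come from seven days of activPAL wear at each of two time points, and baseline testing precedes randomisation.

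Section 16 gives the analysis: "Daily step changes between groups will be compared using a 2 x 2 repeated measures ANOVA, testing for main effects of group and time". The sentence then adds the interaction of group and time. No baseline covariate is named. A mixed model replaces the ANOVA only if attrition is greater than expected, and its handling of baseline is not described. The plan extends to other measures: "Similar analyses will be performed for all other quantitative outcomes described in the Participant Duration section".

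Sections 4 and 16 state 80% power at alpha 0.05 for an effect of about d = 1.06, with 15 dyads per group (Section 4). Section 16 then translates this into steps: "Assuming a SD of approximately 36% and stable control group activity", the effect would be an increase of roughly 35%. Neither section says whether d, or the 36%, refers to the SD of change or the SD of steps at one time point.

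**The concern.** With two time points, the interaction F in a 2 x 2 repeated-measures ANOVA is the square of the two-sample t on change scores. Subtracting baseline fixes the coefficient of baseline at 1. Regression of post steps on baseline estimates that coefficient, and is more precise unless the best coefficient is close to 1. With 30 analysable dyads, precision is scarce, and the baseline measurement is already being collected from everyone.

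The two main effects listed beside the interaction do not answer Aim 2. The group main effect averages each person's baseline and post values. Baseline is taken before randomisation, so it carries no treatment effect and the average halves whatever effect exists. The time main effect pools the two arms, so it picks up any shift common to both. Either could be mistaken for evidence of efficacy if the report does not say which contrast carries the conclusion.

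**Working it through.** **Inputs from the documents.** Alpha 0.05, power 0.80, d about 1.06 (Sections 4 and 16); 15 dyads per group (Section 4); two time points (Section 11).

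**Assumptions.** Two-sided test. d standardised by the SD of change. Equal variances at baseline and post. Rho is not in the documents, so a range is shown.

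**Step 1: the plan's own figure.** Two-sample t-test, noncentrality d × sqrt(n/2) = 1.06 × sqrt(7.5) = 2.90, 28 df. Power is 80.0% and the detectable effect is d = 1.06, so the stated figure reproduces. A one-sided test would give d = 0.93, which supports the two-sided reading.

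**Step 2: variance ratio.** With a common variance s² at each time point:

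- change score: 2s²(1 − rho)
- post adjusted for baseline: s²(1 − rho²)
- ratio: (1 + rho)/2

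**Step 3: small-sample cost.** Estimating the slope leaves 27 residual df and inflates the variance by about 1 + 1/26 = 27/26. Adjusted power therefore uses d = 1.06 / sqrt[(1 + rho)/2 × 27/26] with 27 df. At rho 0.5: 0.75 × 27/26 = 0.779, and 1.06 / sqrt(0.779) = 1.20, giving 88.7%.

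| rho (assumed) | (1+rho)/2 | Power, change score | Power, baseline-adjusted | Detectable d, adjusted |
|---|---|---|---|---|
| 0.3 | 0.65 | 80.0% | 92.6% | 0.87 |
| 0.5 | 0.75 | 80.0% | 88.7% | 0.94 |
| 0.7 | 0.85 | 80.0% | 84.6% | 1.00 |
| 0.8 | 0.90 | 80.0% | 82.5% | 1.03 |
| 0.9 | 0.95 | 80.0% | 80.4% | 1.05 |
| 0.95 | 0.975 | 80.0% | 79.4% | 1.07 |

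Simulation with 20,000 trials per setting agreed within about 1 point, and both tests held their 5% level.

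**Step 4: break-even.** The variances are equal when (1 + rho)/2 × 27/26 = 1, that is rho = 52/27 − 1 = 0.926. Above that, adjustment costs a fraction of a point of power.

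**Step 5: the other reading of d.** If d = 1.06 is on the SD of steps at one time point, change-score against adjusted power is 65.9% against 82.1% at rho 0.3, 80.0% against 88.7% at 0.5, 95.1% against 97.0% at 0.7, and 99.3% against 99.6% at 0.8. The direction is the same. At rho 0.7 and above, the gain is small because power is already high.

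**Step 6: unequal variances.** If the post SD is k times the baseline SD, the variances in units of the baseline variance are 1 + k² − 2·rho·k (change) and k²(1 − rho²) (adjusted). They differ by (1 − k·rho)², so before the slope cost adjustment is never worse. The gain can still disappear. At k = 1.2 and rho 0.7 (both assumed) the variances are 0.760 and 0.734, a saving of 3% instead of 15%. After the factor 27/26 the adjusted variance is 0.763, and nothing is gained.

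**The case against.** The strongest reply is that the plan is already valid. A change-score comparison after randomisation is unbiased with the correct type I error, and the interaction is the contrast that the Section 11 hypothesis describes. It has the stated 80% power at d = 1.06. This is a feasibility study with a preliminary-effects aim, and listing all three ANOVA effects is routine. The gain from adjustment rests on a correlation that the documents do not supply, and it shrinks to nothing at high rho or with a larger post SD. All of that stands, and it is why the point is an improvement and not an error.

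Four stronger readings are tempting, but the documents do not support them.

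- A reader might infer that the plan lacks a test of Aim 2. The interaction is named in the same sentence as the main effects.
- A reader might infer that the ANOVA leaves the trial underpowered. The ratio 35/36 = 0.97 does give 72.9% power if 36% is the SD of change. That shortfall comes from the mismatch between 0.97 and 1.06, which is a separate matter and is not caused by the ANOVA.
- A reader might count three tests at 0.05 and infer a false-positive rate of about 14% (1 − 0.95³, if independent). That needs a rule under which any one of the three counts as success, and the plan states none.
- A reader might infer that attendance and the Intrinsic Motivation Inventory must go through the same ANOVA. Section 16 calls only for similar analyses, and Section 11 gives those measures their own criteria (at least 80%, and a mean above 5.0).

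What remains is that baseline steps are available and unused as a covariate, and that the plan does not say which effect carries the Aim 2 conclusion.

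**Conclusion.** The point holds as a free improvement. The planned interaction is a valid Aim 2 test, but it is usually less precise than a baseline-adjusted contrast on the same data. With d = 1.06 on the SD of change and equal variances, the gain is about 9 points of power at rho 0.5, 5 at 0.7, 2 to 3 at 0.8 and under 1 at 0.9; at 0.95 there is a loss of under 1 point. The size cannot be fixed from the documents, because rho, the SD behind d and the variance ratio are all unstated. The remarks on the two main effects do not depend on rho: one halves the treatment effect and the other is not a between-group comparison.

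**What to change.** In Section 16, define the Aim 2 test as the group coefficient from a regression of post-intervention daily steps on group and baseline daily steps, reported with its 95% CI. If data are missing, use the equivalent mixed model with a common baseline mean across arms. State that the group and time main effects are not used as evidence of efficacy. Use the same contrast for other outcomes measured at both time points. State which SD d = 1.06 refers to and what rho is assumed.

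Cost: SAP wording and one residual degree of freedom, plus a negligible loss of power if rho is about 0.95 or higher. No new data or participants are needed.

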Prompts/Cues (7)	Identification of cues that will be useful in self-management of daily steps moving forward and long-term	Operant Conditioning

intervention. The Fitbit wearable sensor is designed specifically to provide visual physical activity feedback through the Fitbit application. The Fitbit sensor will already be connected to a de-identified account created by the research team prior to distribution to study participants. No GPS data is collected. Fitbit use instructions will be provided verbally and in written form. The Fitbit application will provide the participant feedback on the number of steps he/she has taken during daily living activity and progress toward physical activity goals. The research team will monitor the Fitbit physical activity data through the Fitabase platform (see attachment for Fitabase data security and privacy information).

Research-grade accelerometers (ActivPAL, PAL Technologies, Glasgow, UK)²⁵ will be used to objectively measure physical activity (i.e., daily steps) before and after the 12-week intervention.

Enrolled patient-caregiver dyads (individual with probable amnesic mild cognitive impairment and caregiver) will be randomly assigned to either the intervention group (12-week TPAB intervention) or the control group (usual care/no intervention over 12 weeks). Individuals in the TPAB group will participate in virtual 30-minute weekly sessions for 12 weeks with their primary caregiver and the research interventionist ([name]). Established behavior-change techniques will be used in the TPAB intervention (**Table 1**), based largely on the combination of the Social Cognitive Theory, Control Theory, and Operant Conditioning,²⁶ including behavioral techniques, and patient-centered communication (e.g., motivational interviewing).²⁷ The behavior-change techniques are designed to target and improve daily steps. The patient-caregiver dyads in the control group will receive usual care and no intervention (no Fitbit) over the 12 weeks.

3. Research Objectives

Aim 1: Determine the feasibility of the TPAB intervention for individuals with probable amnesic MCI and their primary caregivers by measuring 1) participant retention, 2) attendance, 3) acceptability (Intrinsic Motivation Inventory)²⁸, 3) safety (adverse event tracking), 4) semi-structured interviews.

Aim 2: Examine the preliminary effects of TPAB on physical activity engagement (daily steps) among MCI participants when compared with the control group.

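### The default daily-steps analysis uses only dyads with both time points, and the intent-to-treat mixed model is held back for dropout above an unquantified level

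*Combined protocol and SAP*

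**What the plan says.** Enrolled dyads "will be randomly assigned to either the intervention group (12-week TPAB intervention) or the control group" (section 3 of the design description, under Background). Section 11 puts baseline testing before randomisation. Section 4 sets the numbers: "Due to anticipated attrition, we plan on recruiting 36 patient-caregiver dyads (18 dyads per group) to meet the necessary 15 dyads per group". Section 16 expects the losses during the 12 intervention weeks, that is, after randomisation.

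For daily steps, section 16 specifies a 2 x 2 repeated measures ANOVA with group, time and their interaction. It adds: "This analysis assumes no missing data for the 15 patient-caregiver dyads". The alternative follows in the same sentence: "in the event of greater than expected attrition occurs, we will use a mixed model to estimate from all available data", on an intent-to-treat basis. Similar analyses are to be used for all the other quantitative outcomes.

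Section 11 separately sets retention of at least 85% as a feasibility benchmark. The document gives no numeric threshold for the switch, no analysis set for the ANOVA, and no handling of missing post-intervention steps when attrition is at or below expectation.

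**The concern.** The plan reserves the analysis of all randomised dyads for the case in which attrition goes worse than planned. In the case it does plan for, some randomised dyads have baseline steps but no post-intervention steps, and the ANOVA cannot use them. The comparison is then between those who stayed in each arm, and randomisation no longer protects it.

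The arms also ask different things of dyads. The intervention arm has twelve weekly sessions with step goals; the control arm has only a weekly call about falls and adverse events. Dropout could therefore differ between arms in number or in kind. The documents do not say who is likely to leave, so this is a possibility and not a prediction.

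At stake is the step contrast, which is the whole of Aim 2 and which section 8 hopes will inform a larger efficacy study.

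**Working it through.** **1. The plan's own sample size figure.** The group-by-time interaction in a 2 x 2 repeated measures ANOVA is equivalent to a two-sample t-test on change scores. With 15 per group, d = 1.06 and two-sided alpha 0.05 (the plan does not state sidedness):
- noncentrality = 1.06 x sqrt(15/2) = 2.903, df = 28, critical t = 2.048
- power = 0.800

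The stated figure is reproduced, and it is built on 15 complete dyads per group.

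**2. How many dyads can fall out before the switch.**
- Section 4: 36 - 30 = 6 dyads, 3 per group, 6/36 = 16.7%.
- Section 11 benchmark, applied to dyads: 0.85 x 36 = 30.6, so at least 31 retained and at most 5 lost.

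**3. The trigger gives different answers on different readings.**

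| Losses (TPAB + control) | Above 3 in an arm? | Above 6 overall? | Above 5 overall (85%)? |
|---|---|---|---|
| 3 + 3 = 6 | no | no | yes |
| 4 + 1 = 5 | yes | no | no |
| 5 + 1 = 6 | yes | no | yes |

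In each row at least one reading calls for the ANOVA and at least one for the mixed model.

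**4. Size of the completers bias when dropout depends on baseline.** Assumptions: no true effect; standardised steps; baseline-post correlation r of 0.5 or 0.7; 18 per arm; the three lowest baseline steppers leave the TPAB arm; three controls leave at random.
- Expected mean of the lowest 3 of 18 standard normal values: -1.41. The remaining 15 then average 3 x 1.41/15 = +0.282.
- Expected change given baseline b is (r - 1) x b.
- Bias at r = 0.5: -0.5 x 0.282 = -0.141 SD. At r = 0.7: -0.3 x 0.282 = -0.085 SD.

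Simulation (4,000 trials per setting) agrees: -0.138 and -0.088 SD, with type I error 0.072 and 0.060. The likelihood estimate, which uses every baseline value, was within 0.003 SD of zero. If all six losses are the lowest baseline steppers in TPAB, the completers bias is -0.26 to -0.15 SD (type I error 0.107 to 0.089), and the likelihood estimate stays within 0.003 SD. If dropout is completely random, both methods are unbiased.

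The plan's scale is "Assuming a SD of approximately 36% and stable control group activity". If that SD is the spread of daily steps between people (the plan does not say), the three-per-arm bias is 0.085 x 36 = 3.1 to 0.141 x 36 = 5.1 percentage points.

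**5. What the mixed model does not repair.** Suppose 3 of 18 TPAB patients leave and gain nothing, and 15 gain 35%. The mean over all randomised is 15 x 35/18 = 29.2%. Simulated estimates (SD 36%, r = 0.5 and 0.7):

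| Who leaves TPAB | All randomised | Completers | Mixed model |
|---|---|---|---|
| unrelated to baseline | 29% | 35% | 35% |
| lowest baseline steppers | 29% | 30 to 32% | 35% |

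The mixed model predicts the missing post values from completers in the same arm, so it cannot see a gain that failed to occur.

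**6. Power.** With 15 post-intervention values per arm, power stays near 0.80, because baseline-only dyads add little about change. With complete data on 18 per arm it would be 0.871.

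**The case against.** Four points can be made for the plan.

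First, the switch and the replacement model are written in advance and depend on attrition, not on step results. That stands: this is not an ad hoc choice of method. What remains is that the threshold has no number, so the rule can be applied only by interpreting it once dropout is known.

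Second, the text never says that dyads will be excluded, and stopping sessions is not the same as missing the post-test. That also stands in part. The loss of 5 or 6 dyads is an inference from the planning numbers and from what the ANOVA needs; it applies only to dyads without post-intervention steps.

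Third, a reader might infer that choosing the ANOVA over the mixed model inflates the effect by 20% (35/29.2 = 1.20). The documents do not support this. That contrast assumes dropouts gain nothing, unobserved, and step 5 shows that the mixed model returns 35% as well. Nor can one infer that the bias favours TPAB: in the baseline-related setting it runs against TPAB, and no section says who will leave.

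Fourth, this is a feasibility trial, Aim 2 is about preliminary effects, and retention is reported in its own right. This limits the severity but does not justify the conditional rule.

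**Conclusion.** The point holds in this form: the default Aim 2 analysis leaves out randomised dyads without post-intervention steps, up to about 5 or 6 of 36 within the attrition the plan expects, and the condition for using all available data is not defined well enough to apply. Nothing elsewhere in the document makes the intent-to-treat analysis unconditional.

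Under the assumptions in step 4 the bias is about 0.08 to 0.14 SD against TPAB, and the mixed model removes it. It would be zero under completely random dropout and could take either sign under other patterns. The correlations and dropout patterns are illustrative and do not come from the plan. The benefit of the change is protection against bias, not power. This is a should-fix point; the trial's feasibility purpose and the modest size of the bias do not make it a must.

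**What to change.** In section 16:
- Make the mixed model on all randomised dyads, by assigned group, the Aim 2 analysis whatever the attrition, and delete the trigger. Fit group, time and their interaction by likelihood, and include dyads that have only a baseline value.
- Report the repeated measures ANOVA on completers as a sensitivity analysis only.
- Add one sensitivity analysis that gives TPAB dropouts the control mean change. With a stable control group and 3 of 18 lost, it would show 29% where completers show 35%.
- Apply the same rule to the other quantitative outcomes that section 16 ties to this analysis.

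In section 11, state that dyads who stop sessions but do not withdraw consent are still asked for the week-13 activPAL wear and post-test. This is the only step that supplies the information the mixed model lacks.

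The sponsor already names the mixed model, so the cost is a few lines of text and trivial analysis work, plus a small effort to post-test dyads who stopped. Section 11 already allows most post-test outcomes to be done in the participant's preferred setting. No sample size changes.
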